8.1.2 Patient prospective cohort

All women who are treated by maternity services at study sites.

The model validation and real-time platform testing datasets sit within this cohort.

8.1.2.1 Inclusion criteria

- All women aged 16 or over who are pregnant.
- At any of the study sites

8.1.2.2 Exclusion criteria

- Patients who have requested that their data not be used for research (e.g., NHS Opt-out, see Section 9.3.1)

8.1.3 MBRRACE-UK cohort

All cases of maternal death and morbidity (for the cohorts described above) collected by MBRRACE-UK (see (65)). This cohort will be used in WS1 and WS2b.

8.1.3.1 Inclusion criteria

- See (65)

8.1.3.2 Exclusion criteria

- See (65)

8.1.4 Patient interviews/Focus groups(escalation pathway)

Women and their partners who have experienced near-miss events or other maternal complications.

8.1.4.1 Inclusion criteria

- Women and their partners aged 16 or over who have experienced near-miss events or other maternal complications.

8.1.4.2 Exclusion criteria

- Women or partners who do not consent.

8.1.5 Staff interviews/focus groups (escalation pathway)

Staff members will be involved in focus groups, interviews and testing the eMOEWS user interface.

8.1.5.1 Inclusion criteria

- Staff members aged 16 or over in a partner hospital.
- Involved in the care, management and escalation of hospitalised women who deteriorate in maternity services.

8.1.5.2 Exclusion criteria

- Staff who do not consent

8.1.6 Staff interviews/focus groups (eMOEWS interface development)

Staff members will be involved in focus groups, interviews and testing the eMOEWS user interface.

8.1.6.1 Inclusion criteria

- Staff members aged 16 or over in a partner hospital.
- Involved in the care, management and escalation of hospitalised women who deteriorate in maternity services.

8.1.6.2 Exclusion criteria

- Staff who do not consent

8.1.7 Staff training (simulation scenarios)

Staff will also take part in scenario simulations (MOET).

8.1.7.1 Inclusion criteria

- Staff members aged 16 or over in a partner hospital.
- Involved in the care, management and escalation of hospitalised women who deteriorate in maternity services.

8.1.7.2 *Exclusion criteria*

- Staff who do not consent

9 PROTOCOL PROCEDURES

9.1 Recruitment

9.1.1 Patients

For the retrospective and prospective cohorts, we will apply for Health Research Authority approval (HRA), under advice from the Research Ethics Committee and the Confidentiality Advisory Group (CAG) to allow access to confidential medical records without specific written consent (Section 251 support).

9.1.2 Staff and public participants

For medical staff we will use purposive sampling to ensure a diverse range of clinical experience, backgrounds, and training. For example, we will work with medical and midwifery leads, and local champions at each trust to identify and invite eligible staff members to participate, along with key NHS IT personnel. We will then snowball from these participants to ensure we are reaching all relevant staff groups.

For public participants we will identify interested women and their partners using posters in our partner hospitals and through our contacts with trusted community support and patient groups.

9.2 Screening and Eligibility Assessment

9.2.1 Patients

- Retrospective and prospective cohorts - there will be no screening in this study.
- Case review cohort – a stratified random sample of cases for review will be computer-generated from each of three partner sites using WP2 pre-anonymisation datasets (post application of the NHS opt-out and patients who have made requests to study sites for their data to be excluded).
- Maternal serious incident cohort – serious incident databases at partner hospitals will be screened for women with clinical maternal serious incident reports.

9.2.2 Staff and public participants

- No screening will occur for staff or public participants – with recruitment occurring as described above.

9.3 Informed Consent

9.3.1 Patients/Public participants

For the retrospective and prospective cohorts, the case review cohort, and the maternal serious incident cohort we will apply for Health Research Authority approval (HRA), under advice from the Research Ethics Committee and the Confidentiality Advisory Group (CAG) to allow access to confidential medical records without specific written consent (Section 251 support).

For the MBRRACE cohorts approvals to use anonymous data for research are already in place.

For public participants in interviews or focus groups, informed consent will also be taken. Women and partners who contact us through our posters or through our written communications or presentations to trusted community support and patient groups will be approached by telephone or in person by an experienced researcher who will explain the purpose of the interviews within the programme of research and provide public participant information. Public participant study documentation will detail the content of the interviews and what interviews will involve for the participant. It will be clearly stated that the participant is free to withdraw from the study at any time for any reason without prejudice to future care, without affecting their legal rights, and with no obligation to give the reason for withdrawal. The participant(s) will personally sign and date the latest approved version of the Informed Consent form. The participant will be given sufficient time up to 28 days to consider the information, and the opportunity to question the Researcher, or other independent parties to decide whether they will participate in the study. Written Informed Consent will then be obtained by means of participant-dated signature and dated signature of the researcher who presented and obtained the Informed Consent Declaration. The person who obtained the consent will be suitably trained and will have been authorised to do so by the Chief Investigator. A copy of the signed Informed Consent declaration will be given to the participant. The original signed form will be retained at the study site.

Face to face interviews will be held in a quiet meeting room. Videoconferencing (using Microsoft Teams or Zoom software) or telephone interviews will be conducted in a private office. The audio from Face to face, telephone and video conferencing interviews will be recorded to allow for transcription.

9.3.2 Staff

For each of eMOEWS interface development, escalation development and simulation scenarios, staff will undergo informed consent. Staff identified through the medical and midwifery leads, and local champions will be approached to take part by telephone or in person by an experienced researcher who will explain the purpose of the interface development groups focus groups, interviews and trialling, escalation focus group or scenario simulation within the programme of research and provide staff participant information. Study staff participant study documentation will detail the content of the component and what the component will involve for the participant. It will be clearly stated that the participant is free to withdraw from the study at any time for any reason without prejudice to future care, without affecting their legal rights, and with no obligation to give the reason for withdrawal. The participant(s) will personally sign and date the latest approved version of the Informed Consent form or Consultant. The participant will be given sufficient time up to 28 days to consider the information, and the opportunity to question the Researcher, or other independent parties to decide whether they will participate in the study. Written Informed Consent will then be obtained by means of participant-dated signature and dated signature of the researcher who presented and obtained the Informed Consent Declaration. The person who obtained the consent will be suitably trained and will have been authorised to do so by the Chief Investigator. A copy of the signed Informed Consent declaration will be given to the participant. The original signed form will be retained at the study site.

Participants will be interviewed or join focus groups at a convenient time and location to them.

Participants will privately confirm their identity to the researcher (e.g., full name, date of birth) at the start of the interview/focus group.

Face to face interviews/focus groups will be held either in a meeting room away from the clinical area or in a quiet room within the clinical care, as chosen by the participant. Videoconferencing (using Microsoft Teams or Zoom software) or telephone interviews will be conducted in a private office. Face to face, telephone and video conferencing interviews will be recorded to allow for transcription.

Audio video recordings of participants may be required to track how participants interact with test user interfaces during eMOEWS interface development.

Audio visually recordings of participants during eMOEWS simulation scenarios will occur in four different training centres across the UK. The video recorded from the four centres will then be sent to a central location. Recordings will then be analysed by at least two members of the research team.

9.4 Randomisation

There will be no randomisation in this study.

9.5 Blinding and code-breaking

There is no blinding or code-breaking in the study.

9.6 Description of study intervention(s), comparators and study procedures (clinical)

There is no intervention in this study.

9.7 Baseline Assessments

Not applicable.

9.8 Subsequent Visits

Not applicable.

9.9 Sample Handling

No sample will be taken during the course of this study.

9.10 Early Discontinuation/Withdrawal of Participants

This is an observational study. Participants can request their data to be deleted at any time in accordance with GDPR and the study privacy policy.

9.11 Definition of End of Study

The end of study described in this protocol is the point at which all the study data has been entered, the eMOEWS built and checked and any post-implementation changes to eMOEWS algorithm have been added to the final derived and validated eMOEWS.

10 SAFETY REPORTING

This is a non-interventional study, so safety reporting is not applicable.

11 STATISTICS AND ANALYSIS

11.1 Statistical Analysis Plan (SAP)

The statistical aspects of the study are summarised here, with details fully described in a statistical analysis plan that will be publicly available from the time the first retrospective dataset is extracted from a minimum of 3 hospitals. The SAP will be finalised before any statistical analysis takes place.

11.2 Description of the Statistical Methods

11.2.1 Workstream 1

We will report descriptive statistics describing the proportion of women meeting each of the new criteria and in total in WS2 retrospective datasets – comparing these proportions relative to the hospital populations with published rates for our individual criteria,

We will use descriptive statistics to report the proportions of events correctly captured by our new electronic definitions in the stratified sample cohort and events missed in our review of hospital systems for recording serious events.

Similarly, from MBRRACE-UK we will report the proportions of women who meet the new definitions.

11.2.2 Workstream 2a

We will describe the characteristics of the study population and compare to national figures to ensure it is appropriately diverse and representative. To assess the predictive performance of each MOEWS/MEWS (11), we will report sensitivity and specificity at pre-defined thresholds, and overall score discrimination (c-statistic). Calibration, the level of agreement between observed outcomes and a model's predictions, is a key aspect of assessing predictive performance for prognostic models. However, a weakness of existing MOEWS is that they generally do not provide an estimate of risk, therefore, assessment of calibration will not be possible. We will, however, calculate the risk of our key events according to each level of MOEWS. We will also compare how early each MOEWS alerts prior to events. We will use the new multi-site dataset to calibrate the centile-based national MOEWS we developed with NHSE/I.

We will also explore whether MOEWS performance varies between key sub-groups (e.g., age, ethnicity), to identify where groups could be disadvantaged, or where the MOEWS could be improved. We will report the rates of missing vital sign data and use different approaches to account for these missing values during analysis (e.g., complete cases, assuming all missing values are normal or abnormal, and multiple imputation), to check the robustness of our estimates.

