6 OBJECTIVES AND OUTCOME MEASURES

| Objectives | Outcome Measures | Timepoint(s) of evaluation of this outcome measure (if applicable) |
|---|--|--|
| Primary Objective To develop and validate an electronically embedded, data-enhanced Maternal Early Warning Score (eMOEWS) with clinical escalation pathways | Predictive performance of new early warning scores, assessed by: discrimination, calibration, and clinical utility. | During pregnancy or in the immediate postpartum period. |
| Secondary Objectives: | | |
| To define 'near-miss' and 'pre-near-miss' criteria for use with routinely-collected data to measure maternal outcomes. | 'Near-miss' and 'pre-near-miss' outcome criteria measurable using routinely available electronic data, assessed in NHS hospitals | During pregnancy or in the immediate postpartum period. |
| To assess performance of the new near-miss and pre-near-miss outcome criteria in 3 hospitals and MBRRACE-UK: 
 • a stratified random sample of 100 sets of records of near-miss and pre-near-miss cases across the three sites. • review hospital serious event systems for serious maternal events • Proportions of women meeting criteria | Descriptive statistics to describe whether the electronic criteria used correctly identified the conditions. Descriptive statistics of missed and captured events according to electronic criteria Descriptive comparison to published rates | During pregnancy or in the immediate postpartum period |
| To develop a large representative eight-twelve maternity unit cohort | Cohort developed and ready for assessment | 05/2029 |

| | | |
|--|--|---------|
| for model development and assessment | | |
| To investigate the performance of existing MOEWS/MEWS scores in the new maternity cohort and in women who have died or had severe morbidity in pregnancy | Evidence-based assessment of existing MOEWS, both in new retrospective (assessed by discrimination, risk of our key events at each MOEWS/MEWS level) and nationally recognised mortality/morbidity (assessed by sensitivity and duration of prior warning) cohorts | 05/2029 |
| To develop and validate an optimal vital-signs-only-based MOEWS | Relative performance of new MOEWS, best published MOEWS and NHSI national MOEWS for prediction of near-miss or pre-near-miss | 05/2029 |

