7.3.3 Workstream 2b

7.3.3.1 Participants

MBRRACE-UK undertakes confidential enquiries into maternal deaths and specific severe morbidities. We have already extracted event and vital sign data for 205 women who died or suffered severe morbidity (from pulmonary embolism and severe haemorrhage). In this work stream, we will additionally extract available re-laparotomy (n=32) and diabetic ketoacidosis cohorts (n=80) to complete representation of the available major reversible events. We will also extract additional outcome data to define when women meet the new 'near-miss' and 'pre-near-miss' criteria (WS1). This will require an extended output request to the Healthcare Quality Improvement Partnership. All women in the cohort are likely to have had one of the near-miss or pre-near-miss events (as defined in WS1) or death.

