11.2.3 Workstream 2b

We will summarise key characteristics of women who experience these events, including demographics, clinical characteristics, vital signs measurements, and type of event. We will describe when women in MBRRACE-UK meet the new outcome criteria, prior to the extreme outcomes that result in inclusion in

the MBRRACE-UK dataset. For each existing MOEWS/MEWS, we will calculate sensitivity at pre-defined thresholds and assess how early women alert prior to the events occurring, if at all. Where sufficient data exist, we will examine performance in key subgroups. Missing vital sign data will be handled similarly to WS2a.

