11.2.4.3 Assessment of model performance

The performance of both new models will be assessed through internal and external validation. The performance of a model in the development data is usually over-estimated. Internal validation techniques will be used to adjust for this ‘optimism’. The internal validity of the final models will also be assessed by the bootstrap re-sampling or k-fold cross validation techniques to adjust for over-optimism in the estimation of model performance. To ensure a meaningful comparison we will use the same internal validation procedures to compare statistical and machine learning models. The internal validation will quantify and be used to adjust the performance measures (e.g., discrimination, calibration) for any optimism. Heterogeneity in model performance will be explored across different hospitals using internal-external cross-validation (71).

We will use the performance metrics used in WS2 (i.e., discrimination, sensitivity, specificity, and the degree of advanced warning prior to an event). As discussed above, the performance of a prediction model is typically characterised by assessing both its calibration and discrimination. With our new models we will be able to assess model calibration as the new development models will provide risk estimates. Calibration reflects how close the predictions from the model are to the observed outcome frequencies, so represents a major step forward in assessing eMOEWS performance. It is a key performance metric recommended in TRIPOD (Transparent reporting of a multivariable prediction model for individual prognosis or diagnosis) guidance (72). Calibration will be assessed graphically, using a calibration plot, plotting observed outcomes against predictions using smoothing techniques. The plot will also be supplemented with results for individuals grouped by similar probabilities (tenths) comparing the mean predicted probability to the mean observed outcome. Calibration will also be quantified by calculating the calibration slope and intercept. The discrimination of the prediction models will be summarised with the concordance statistic (equivalent to the Area Under Receiver Operating Characteristic curve) with 95% confidence interval. Validation will include assessing for variation in performance between key sub-groups, as per WS2.

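### Lead time, and sensitivity in the event-only WS2b cohort, are assessed across scores with no common operating point, so differences can reflect alert burden rather than better early warning

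*Protocol*

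**What the plan says.** **WS2a (section 11.2.2).** Existing scores are evaluated in the retrospective cohort by sensitivity and specificity at pre-defined thresholds and by the c-statistic. Two further commitments follow: "We will, however, calculate the risk of our key events according to each level of MOEWS", and "We will also compare how early each MOEWS alerts prior to events".

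**WS2b (section 11.2.3).** In the MBRRACE-UK data, for each existing score, "we will calculate sensitivity at pre-defined thresholds and assess how early women alert prior to the events occurring, if at all". The objectives table in section 6 names the same pair of measures for the "nationally recognised mortality/morbidity (assessed by sensitivity and duration of prior warning) cohorts". On who is in this cohort, section 7.3.3.1 says: "All women in the cohort are likely to have had one of the near-miss or pre-near-miss events (as defined in WS1) or death".

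**WS3b (section 11.2.4.3).** The WS2 measures are carried forward to the new models: discrimination, sensitivity, specificity and "the degree of advanced warning prior to an event". Calibration is added for the new models, and decision curve analysis is added for the comparison with published scores.

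The protocol nowhere ties lead time, or WS2b sensitivity, to a common specificity, alert rate or number of alerts per event. Section 11.1 leaves details to a SAP that is not shown.

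**The concern.** Time from the earliest alert to the event depends on two things: how well a score separates deteriorating women from others, and how often it alerts at all. A score that triggers often will trigger early in most women, including those who later have an event, even if it carries no information. Sensitivity behaves in the same way. Unless operating points are aligned, a longer lead time cannot be read as better early warning.

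WS2b is the more exposed setting. With essentially no women free of events, specificity and false-alert burden cannot be estimated there, and neither of its two measures can penalise a score for alerting too often. A SAP cannot repair this from WS2b data alone, because the cut-offs have to come from WS2a. The protocol does not plan that link.

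At stake is any statement that one score warns earlier than another, both among existing tools and, in WS3b, between the new models and the published ones.

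**Working it through.** The protocol gives no figure for lead time, alert rate or WS2b sensitivity, so there is nothing of its own to reproduce on this point. Two inputs come from it:

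- WS2b size: section 7.3.3.1 itemises 205 women already extracted, 32 re-laparotomy and 80 diabetic ketoacidosis cases, so 205 + 32 + 80 = 317. The 1,300 in the synopsis is the whole MBRRACE-UK cohort, which also serves WS1.
- Event rate: 2% (section 11.3.2).

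Observation frequency, alert rates, drift and correlation below are assumptions.

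**1. A score with no information.** Assume 12 observation sets at four-hour intervals over the 48 hours before the event, each alerting independently with probability a.

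- Proportion of events detected = 1 − (1 − a)^12.
- Mean lead, counting no alert as zero = Σ a(1 − a)^i × 4(12 − i) for i = 0 to 11, which equals 4 × [12 − (1 − a)(1 − (1 − a)^12)/a].

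For a = 0.05: detected = 1 − 0.95^12 = 0.46; lead = 4 × [12 − 0.95 × 0.4596/0.05] = 4 × 3.27 = 13.1 h.

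For a = 0.20: detected = 1 − 0.80^12 = 0.93; lead = 4 × [12 − 0.80 × 0.9313/0.20] = 4 × 8.275 = 33.1 h.

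Specificity per woman over the same 12 sets falls from 1 − 0.46 = 0.54 to 1 − 0.93 = 0.07, which an event-only cohort cannot show.

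Halving the window to 24 hours with 6 sets gives the same direction. Raising a from 0.02 to 0.30 raises sensitivity from 0.11 to 0.88 and mean lead from 1.6 h to 15.8 h.

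**2. One informative score, threshold moved.** Simulation of 200,000 women with and 200,000 without events, with 6 four-hourly sets, within-woman correlation 0.5, a linear drift before the event, and a c-statistic of 0.886. Lowering the threshold from 2.5 to 0.5 gives:

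| | Threshold 2.5 | Threshold 0.5 |
|---|---|---|
| Sensitivity | 0.43 | 0.98 |
| The same, out of 317 women | 137 | 312 |
| Mean lead, all event women | 4.2 h | 19.1 h |
| Specificity | 0.97 | 0.32 |
| Positive predictive value at 2% | 23% | 3% |

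Only the first three rows could be obtained from WS2b.

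**3. Two scores, unmatched and matched.** Same simulation, with a better score (c 0.886) and a worse one (c 0.752).

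| Operating point | Score | Sensitivity | Mean lead, all event women |
|---|---|---|---|
| Specificity 0.90 | Better | 0.657 | 7.7 h |
| Specificity 0.55 | Worse | 0.798 | 13.0 h |
| Matched at 0.90 | Better | 0.665 | 7.8 h |
| Matched at 0.90 | Worse | 0.378 | 4.6 h |

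Unmatched, the worse score leads on both measures. Matched, the true order returns.

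The reversal is not automatic. With the better score at specificity 0.76 and the worse still at 0.55, the better score is ahead on sensitivity (0.837 against 0.798), although its mean lead is still shorter (11.8 h against 13.0 h).

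**4. Women who never alert.** At matched specificity 0.90, mean lead among alerting women only is slightly longer for the worse score (12.1 h against 11.7 h). Leaving out women who never alert would therefore bring back part of the problem that matching removes.

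**The case against.** The strongest reply has four parts.

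- **Thresholds.** A reader might infer that each tool will be run at its own trigger levels. The text says only that thresholds are pre-defined, and the unseen SAP could set them at a common specificity. That stands: the supportable statement is that no common operating point is given.
- **Other measures.** A reader might infer that over-alerting goes unmeasured. It does not. In WS2a, specificity, the c-statistic and risk per level would expose an uninformative score, and WS3b adds decision curves, which charge for false positives. That stands for visibility. But none of these adjusts the lead-time comparison, and WS2b has none of them.
- **Choice of comparator.** A reader might infer that an over-alerting score could be named the best published MOEWS on lead time. The protocol does not make lead time or WS2b a selection criterion. For the retrospective cohort, section 6 lists discrimination and risk by score level, and section 11.2.4.3 refers the WS3b comparison to performance from WS2a. That reading is not supported.
- **Published triggers.** For tools already in clinical use, performance at published trigger points is a legitimate main result. That stands, and the matched comparison should be added to it rather than replace it.

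It can also be said that WS2b announces no ranking and that alerts within a woman are correlated, which weakens the independent-sets arithmetic. Both are fair. Yet WS2b computes the same two measures for every score under an objective about their performance, so readers will compare them. The simulation with correlation 0.5 shows the same direction.

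**Conclusion.** The point holds as an inexpensive improvement to the analysis, not as an error that invalidates the plan. The protocol commits to comparing how early scores alert, and restricts WS2b to two measures that rise with alert frequency, in women who nearly all had an event. Differences in lead time (WS2a, WS2b, WS3b) and in WS2b sensitivity can therefore reflect alert burden.

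The direction does not depend on the assumptions; the size does. The move from 46% and 13.1 h to 93% and 33.1 h assumes 12 independent four-hourly sets and alert rates of 5% and 20%, none of which comes from the protocol. It would be tempting to conclude that the planned comparison will put the wrong score ahead. The documents do not support that, because real alert rates are unknown and the bias is a tilt that need not change the order.

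**What to change.** State in the SAP, and where useful in sections 11.2.2 to 11.2.4.3:

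1. Report results at the pre-defined or published thresholds as planned.
2. In addition, compare lead time and sensitivity at a common specificity or alert rate, estimated among women without events in WS2a.
3. Carry those cut-offs unchanged into WS2b and into the WS3b comparison, and set the new models' cut-offs by the same rule.
4. Count women who never alert as zero lead.
5. Base any statement that one score warns earlier than another on the matched comparison.

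The cost is some extra analysis on data already planned for. The drawback is that coarse or colour-trigger scores offer few operating points, so matching for them will be only approximate; the specificity or alert rate actually achieved should be shown beside each result.
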